4.3.2 Concomitant Medications

All subjects must have been stabilized on optimal doses of conventional PAH therapies (e.g., oral vasodilators, digoxin, diuretics, oxygen, anticoagulants) for at least 10 days prior to Baseline assessments. The exceptions are the discontinuation or dose changes of anticoagulants and/or dose change of diuretics. After randomization, additions, deletions, and dose changes may occur if the Investigator determines it is medically necessary. For the purposes of the 6MWT, if the subject was assessed at Baseline using oxygen therapy then all future 6MWTs during the study must be conducted with the same oxygen flow rate and mode of administration; any changes in oxygen therapy administration should be noted in the eCRF.

All concomitant medications taken during conduct of the study, including those taken for AEs or other medical events, should be recorded in the subject's source documents and transcribed as required to the eCRF.

5 SUBJECT ENROLLMENT

5.1 TREATMENT ASSIGNMENT

Eligible subjects will be randomly allocated to receive either UT-15C or placebo at randomization. During the Screening period a screening number will be assigned using an electronic data capture (EDC) system to identify individual subject data until the subject is randomized. Upon randomization, each subject will be assigned a new unique study subject number via the IVRS/IWRS. The IVRS/IWRS will also be responsible for allocation of all study drug.

5.2 RANDOMIZATION

The study will be randomized 1:1 UT-15C to placebo. All subjects will be randomly allocated to receive UT-15C or placebo through the IVRS/IWRS using a centrally administered stratified permuted block randomization by type of background therapy (Strata 1: PDE5-I and sGC stimulator; Strata 2: ERA) which will be balanced across the two treatment groups. Subjects will also be stratified by Baseline 6MWD (less than or equal to 350 meters and greater than 350 meters). Block sizes will be variable and not disclosed to Investigators so that no inferences can be made about possible treatment assignments of current or future subjects.

Prior to randomization, site personnel should complete a Pre-Baseline Review Form for review and approval by the Medical Monitor.

5.3 BLINDING

The Investigator, study site, subject, and sponsor will not be aware of the treatment allocation. All clinical trial material (CTM) will be provided as blinded study drug. See Section 6.2 for the procedure for unblinding subjects at the end of study to determine appropriate starting dose for the open-label study (TDE-PH-311).

6 DRUGS AND DOSING

6.1 DRUG DOSAGE, ADMINISTRATION AND SCHEDULE

The UT-15C tablets are sustained release osmotic tablets. Active treatment is UT-15C tablets provided as 0.125, 0.25, 0.5, 1, and 2.5 mg strengths. The 0.125, 0.25, 0.5, 1, and 2.5 mg tablets are colored blue, green, white, yellow, and pink, respectively. The formulation contains

pharmaceutically acceptable excipients used in other approved drug products. Placebo tablets are identical in size, shape, and color to the respective UT-15C tablets.

Once all entry criteria have been met and random treatment assignment confirmed, the first dose of study drug (0.125 mg) should be taken at the site by the subject immediately after (~10 minutes) consuming food. Oral dosing of study drug will be continued at 0.125 mg TID (every 6 to 8 hours) immediately after (~10 minutes) consuming food. Subjects must be instructed to take the appropriate amount of UT-15C tablets based upon their prescribed dose. Prior to the Week 4 visit, each dose of study drug should be adjusted in 0.125 mg increments every 24 hours as clinically indicated. Following the Week 4 visit throughout the remainder of the study, each dose of study drug may be adjusted in 0.125 or 0.25 mg increments every 24 hours as clinically indicated. The maximum allowable dose of study drug will be 12 mg TID.

Doses of study drug should continue to be increased in the absence of dose-limiting drug-related adverse effects, to ensure that each subject receives the optimal clinical dose throughout the study. [Table 6-1](#) provides a range of doses that may be reasonable targets for a subject to achieve by visit notwithstanding any AEs that limit dose escalation.

Table 6-1 Study Drug Goal Dose Titration Ranges

Study Week	Dose (mg) Three Times Daily
4	0.5 – 1.5
8	1.5 – 2.5
12	2.5 – 3.5
24	5.5 – 6.5

Dose changes should be conducted under appropriate medical supervision in consultation with the study site. Each dose of study drug is not required to be the same during titration. For example, doses of 1.125 mg morning, 1.125 mg afternoon, and 1.25 mg evening, are acceptable during titration. It is recommended that the difference between any of the three doses not exceed 0.125 mg prior to Week 4 or 0.25 mg after Week 4.

At least weekly telephone calls between site personnel and the subject should be made during the first 24 weeks of the study to monitor AEs and make decisions about dose titration. More

frequent telephone calls may be necessary depending on the frequency of dose titration and to manage AEs or signs and symptoms of disease. If dose titration is considered appropriate, site personnel will instruct the subject to modify their dose. Study drug dosing should be recorded at each study visit between Baseline and Week 24. Dose changes between Baseline and Week 24 will be recorded in source documentation and the subject's eCRF by site personnel. Beyond Week 24, study drug dose will be recorded on the day of Continued Visits (e.g. Weeks 36, 48, etc.) and every 30 days between Continued Visits in source documentation and the eCRF by site personnel. If it becomes necessary for a subject to modify their dose (e.g., due to an AE) without prior instructions from site personnel, the subject should be instructed to contact the site as soon as possible and report any dose changes to site personnel for updating in source documentation and the eCRF as appropriate.

After Week 24, at least monthly telephone calls should be made to continue to monitor AEs and make decisions regarding appropriate dose titrations. More frequent telephone calls may be necessary depending on the frequency of dose titration and to manage AEs or signs and symptoms of disease. Site personnel should record all dose changes in source documentation from Week 24 until Study Termination.

In the event a subject requires to be permanently discontinued from study drug (e.g. as a result of clinical worsening or the subject wishes to withdraw from further participation in the study), the Investigator should conduct the study drug termination assessments and then gradually down titrate the study drug, taking into consideration the subject's clinical condition, current study drug dosing regimen, and previous clinical response to study drug.

Throughout the course of the study, the dose of study drug should continue to be increased at the discretion of the Investigator up to a maximum allowable dose of 12 mg TID. Dose escalation may be made less frequently or temporarily suspended if a subject experiences an intolerable AE that may worsen as a result of an increase in study drug dose. If an AE remains intolerable, the Investigator may decrease the dose of study drug. In the event of continued intolerable AEs, dose reductions may occur. The exact dose reduction and frequency of dose reduction should be based on the clinical condition of the subject and the severity/seriousness of the event. In general, dose reductions may occur in 0.125 mg or 0.25 mg increments every 12 to 24 hours.

Larger dose reductions may be necessary in the event of an emergency situation. If the subject is still experiencing an intolerable AE then the Investigator may temporarily or permanently withdraw the subject from study drug. Following temporary discontinuation of study drug, all attempts should be made to re-initiate study drug in affected subjects. Subjects should be re-started on study drug at a reduced dose or at 0.125 mg TID depending on the clinical condition of the subject, the subject's previous response to study drug, the dose at the time of discontinuation, and the duration of temporary discontinuation from study drug. Following restart of study drug, all efforts should be made to increase the dose until the desired clinical improvement in the subject's symptoms of PAH occurs.

Notwithstanding these study drug dosing guidelines, the well-being of each subject is paramount and all Investigators must act in accordance with the best medical interests of the subjects at all times during their participation in the study.

6.1.1 Dosing of Study Drug in Relation to Meals

Subjects should take study drug approximately every 6 to 8 hours with approximately 240 mL (8 ounces) of water or other beverage (e.g. juice, milk, soda, etc.) immediately after (~ 10 minutes) consuming food.

Subjects should be instructed to be careful not to break, chew, or disrupt the integrity of the tablet as this will result in inappropriate delivery of the active ingredient. If the tablet is inadvertently damaged during administration, the subject should contact site personnel in order to be monitored for the onset of symptoms due to possible overdose. Any tablet damaged during handling by the subject should not be consumed by the subject. The subject should be instructed to notify the study personnel and return the damaged study drug at the next scheduled visit.

6.1.2 Dosing and Administration of Adjunctive Medications

Every subject must be receiving one PAH-approved oral monotherapy (e.g., sildenafil, tadalafil, bosentan, ambrisentan, macitentan, or riociguat) for at least 30 days prior to randomization and on the same dose for at least 10 days prior to randomization. Dosing of background PAH-approved oral monotherapy must comply with the prescribing information for the product.

All attempts should be made to adjust the dose of study drug rather than the dose of PAH-approved oral therapy to obtain the desired clinical response. Throughout the course of the study, dose and frequency of the PAH-approved oral therapy may not be increased to compensate for lack of efficacy. Similarly, the dose and frequency of PAH-approved oral therapy should not be reduced during the study unless it is considered medically necessary to protect the safety of the subject. If the dose of PAH-approved oral therapy is inadvertently titrated during the course of the study, the dose should be titrated back to the dose used at the time of randomization, if medically appropriate. If the dose of PAH-approved oral therapy is increased during the Treatment Phase and is not subsequently titrated back to the dose used at the time of randomization, the subject will need to be removed from the study.

In the event a subject must undergo a change in background therapy, they should be switched to another agent in the same PAH-approved medication class if possible. If another agent in the same class is not available, the subject should be switched to an agent from another class of PAH-approved medication. If no alternative therapy is available, the subject will continue in the study until either a clinical worsening event has occurred, the subject withdraws from the study, or the study is completed/discontinued.

All subjects must have been stabilized on optimal doses of conventional PAH therapies (e.g., oral vasodilators, digoxin, diuretics, oxygen, anticoagulants) for at least 10 days prior to randomization. The exceptions are the discontinuation or dose changes of anticoagulants and/or dose change of diuretics. After randomization, additions, deletions, and dose changes may occur if the Investigator determines it is medically necessary.

6.2 ACCESS TO BLINDED TREATMENT ASSIGNMENT

During the study, neither the site personnel, subject, nor sponsor should be unblinded to the treatment assignment of any subject for any reason except in the event of a medical emergency (e.g., a life threatening event), if and when knowledge of the treatment assignment is considered necessary to determine the optimal medical management. Appropriate communications should take place between the site and the sponsor before accessing the IVRS/IWRS to allow unblinding of a subject's treatment assignment. In the event of a medical emergency that requires immediate

unblinding, the IVRS/IWRS may be accessed by the Investigator to determine treatment assignment.

Subjects who remain on study drug, complete required study assessments, and meet the definition of clinical worsening will be eligible for an open-label study (TDE-PH-311). Subjects requiring long term treatment (29 days or more) with infused or inhaled PGI₂ for treatment of worsening PAH are not eligible for the open-label study. Following completion of the Study Drug Termination assessments for a subject (see [Table 3-1](#)) and entry of required data into the IVRS/IWRS, the site personnel will be unblinded to that subject's treatment assignment. If the subject received UT-15C during the study then the subject may remain on the same dose of study drug upon entry into the open-label study. If the subject received placebo during the study then the subject should start treatment with UT-15C in the open-label study in accordance with that protocol.

Subjects who permanently discontinue study drug for any reason other than meeting the definition of clinical worsening are not eligible for entry into the open-label study. The site personnel will not be unblinded to the treatment assignment of these subjects unless required for safety reasons.

Following completion of all Study Drug Termination assessments (see [Table 3-1](#)) and entry of required data into the IVRS/IWRS, the site personnel will be unblinded to that subject's treatment assignment at the time of enrollment into the open-label study. After approximately 205 adjudicated clinical worsening (morbidity or mortality) events have occurred, all ongoing subjects will be eligible for enrollment in the open-label study or gain access to drug commercially if approved.

6.3 COMPLIANCE

The Principal Investigator or other site personnel under the direction of the Principal Investigator will be responsible for dose titration of study drug and recording all dosing information in source documents. During telephone calls, site personnel will record the current dose of study drug and determine if the subject is taking study drug as prescribed.

Each subject will be provided with a dosing diary in order to record dosing information from Randomization until Week 24; the use of the dosing diary is optional after Week 24. At scheduled study visits, subjects should be instructed to bring all study drug (including empty and unused bottles) and their dosing diary to the investigational site. Upon return of study drug and dosing diary at the Week 4, 8, 12, and 24 visits, the study coordinator or pharmacist must document the number of returned tablets of each strength and determine if the appropriate amount of study drug remains based upon the dose of study drug prescribed. Each subject will also be asked at each visit whether he or she has been compliant with dosing instructions. Subject compliance with the prescribed dosage regimen will be monitored throughout the study. If it is determined that a subject is not compliant with study drug then site personnel must re-educate the subject on proper dosing compliance and its importance. Continued non-compliance may lead to withdrawal of the subject from the study, after consultation between the Investigator and the Sponsor.

Upon return of study drug at all protocol-required on-site study visits (e.g. Weeks 4, 8, 12, 24, etc.), all bottles of study drug will be collected. Study drug returned will not be re-dispensed to the subject. Site personnel will dispense a new supply of study drug at each protocol-required visit for the subsequent interval. If necessary, additional study drug may be dispensed in between protocol-required visits.

7 EXPERIMENTAL PROCEDURES

7.1 SCREENING PHASE

Sites may conduct pre-Screening activities prior to a specific subject signing an informed consent. Pre-Screening activities may include review of the site's database to identify potential patients that may be eligible for the study. The Screening Phase will be conducted within 30 days prior to randomization and after informed consent has been obtained. The Screening and Baseline assessments may be conducted in one visit if all assessments are performed and all entry criteria are satisfied within the 48 hours prior to randomization and dosing with study drug.

The recommended sequence of events for Screening assessments are displayed below:

- Informed consent
- Inclusion/exclusion criteria
 - If necessary, the following procedures may be performed during the 30 day Screening window if required to satisfy inclusion/exclusion criteria.
 - RHC
 - Echocardiography
 - Ventilation Perfusion Scan
 - High Resolution Computerized Tomography (CT) Scan
 - Multigated angiogram (MUGA)
 - Pulmonary Angiography
 - Pulmonary Function Tests
 - Previous medical records documenting eligibility criteria may also be used provided the previous records document subject eligibility within the protocol mandated timelines, as applicable.
- Demographics
- PAH history
- Medical history
- Vital signs (following at least 5 minutes of rest)
- Physical examination
- 12-lead ECG (following at least 5 minutes rest in the semi-recumbent position)
- Practice 6MWT/Borg dyspnea score (*optional*; serves as a practice test if the subject has not previously performed this test at the study site; 6MWT to be conducted following at least 5 minutes of rest and Borg dyspnea score to be conducted immediately following 6MWT)
- Clinical laboratory tests
- Urine pregnancy test (for WOCBP)
- Concomitant medications
- AE assessment
- Complete and submit Pre-Baseline Review Form

7.2 BASELINE VISIT

The recommended sequence of events for the Baseline Visit is displayed below:

- RHC (optional; must be performed within 5 days before randomization (inclusive) and on one stable PAH-approved oral monotherapy for a minimum of 10 days prior to RHC)
- Confirmation of inclusion/exclusion criteria
- Vital signs (following at least 5 minutes of rest); including height
- WHO Functional Class for PAH
- AE assessment
- 6MWT/Borg dyspnea score (6MWT to be conducted following at least 5 minutes of rest; Borg dyspnea score to be conducted immediately following 6MWT)
- Clinical laboratory tests/NT-proBNP
- Urine pregnancy test (for WOCBP)
- Randomization (to be performed after all other Baseline assessments are completed)
- First administration of study drug immediately (~10 minutes) after consuming food
- Drug accountability
- Concomitant medications
- At least weekly telephone calls begin following initiation of study drug up to Week 24 of treatment, to monitor compliance, AEs, use of concomitant medications, occurrence of clinical worsening and to make decisions regarding dose titration

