- ^a The Screening and Baseline assessments may be combined if all entry criteria are satisfied within 48 hours prior to randomization. Sites should provide a completed Pre-Baseline review form to the Medical Monitor which will be reviewed, signed and returned to the site prior to randomization. Sites may conduct pre-Screening activities prior to a specific subject signing an informed consent. Pre-Screening activities may include review of the site’s database to identify potential patients that may be eligible for the study.
- ^b Vital signs should be conducted prior to, or at least 30 minutes following, the corresponding 6MWT. Subjects should rest for 5 minutes prior to collection of vital signs
- ^c If the subject has not previously undergone a 6MWT at the study site, a practice 6MWT must be conducted during the Screening period
- ^d Subject should rest for 5 minutes prior to each 6MWT. All 6MWTs following randomization must be conducted 3 to 6 hours after the last dose of study drug
- ^e During the Continued Visits, laboratory samples and NT-proBNP will only be collected at the first Continued Visit and at every other Continued Visit thereafter
- ^f To be conducted following a minimum of 5 minutes rest in the semi-recumbent position
- ^g To be conducted within 5 days prior to Randomization (inclusive) and following a minimum of 10 days on stable background PAH oral monotherapy
- ^h To be conducted within 72 hours after all other Week 24 assessments; as best as possible to be performed 3 to 6 hours after previous dose of study drug
- ⁱ First dose of study drug will be administered in the clinic following randomization; study drug dosing will continue at 0.125 mg TID (every 6 to 8 hours)
- ^j The window for Week 4, 8, 12 and 24 visit assessments is ± 7 days; the window for visits following Week 24 is ±14 days.
- ^k At any time during the Treatment Period, subjects may return to the study site for additional assessments as required

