3.2.1.2.1 Practice Six Minute Walk Test

All subjects must have a documented 6MWT conducted at the study site on the course intended for use during the study. If no previous 6MWT has been performed at the study site, a practice 6MWT must be conducted at least 1 day prior to the Randomization 6MWT for applicable subjects.

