3.2.1.2.2 Baseline Six Minute Walk Test

A Baseline 6MWT must be performed prior to initiation of study drug and should be conducted on the day of randomization. The Baseline 6MWT must be conducted no earlier than 1 day following the practice 6MWT, for applicable subjects. Once the Baseline 6MWT has been

conducted, the site will enter the subject's six-minute walk distance into an interactive voice or web response system (IVRS/IWRS). IVRS/IWRS will confirm to site personnel the subject's eligibility to participate in the study based on 6MWD, and if eligible, randomize the subject into a treatment group and allocate appropriate study drug.

3.2.1.2.3 *Treatment Six-Minute Walk Tests*

6MWTs will be conducted at Weeks 4, 8, 12, 24, and every 12 weeks thereafter. The 6MWT should be conducted 3 to 6 hours following the last dose of study medication. Subjects receiving supplemental oxygen during the Baseline 6MWT must continue to receive the same flow rate and mode of oxygen therapy at all subsequent 6MWT assessments; any changes in oxygen therapy administration should be noted in the eCRF. In addition, subjects receiving pulmonary rehabilitation prior to study entry should continue on the same schedule up to and including Week 24. Following Week 24, pulmonary rehabilitation may be adjusted per standard of care. Pulmonary rehabilitation may not be added to a subject's regimen between randomization and Week 24. Documentation of pulmonary rehabilitation should occur in the special circumstances section of the eCRF. Additional 6MWTs may be conducted as appropriate throughout the course of the study for the purposes of evaluating clinical worsening status.

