Plasma NT-proBNP concentration is a useful biomarker for PAH as it is associated with changes in right heart morphology and function [Fijalkowska 2006]. NT-proBNP sample collection will occur at Baseline (prior to starting study drug), Week 12, Week 24, the first Continued Visit, and every other Continued Visit thereafter (i.e., Continued Visits #3, #5, #7, etc.). NT-proBNP will also be assessed at the Study Drug Termination visit.

3.2.1.6 *Right Heart Catheterization (Optional Assessment)*

This section describes the optional RHC assessments that may be conducted at Baseline and Week 24.

If a subject agrees to participate in the optional hemodynamic assessments, a RHC must be performed within 5 days before randomization (inclusive). The subject must be on stable

background therapy for a minimum of 10 days prior to this RHC. If a RHC is performed on the day of randomization, all other study-related assessments, other than initiation of study drug, should be performed prior to conduct of the RHC. A follow-up RHC must be performed within 72 hours following completion of Week 24 assessments. As best as possible, follow-up RHC should be performed within 3 to 6 hours of previous dose. Hemodynamic parameters to be assessed and recorded include heart rate (HR), systolic systemic arterial pressure (SAPs), diastolic systemic arterial pressure (SAPd), mean systemic arterial pressure (SAPm), systolic pulmonary artery pressure (PAPs), diastolic pulmonary artery pressure (PAPd), mean pulmonary artery pressure (PAPm), mean right atrial pressure (RAPm), mean pulmonary capillary wedge pressure (PCWPm), cardiac output (CO), arterial oxygen saturation (SaO₂), and mixed venous oxygen saturation (SvO₂). Additional hemodynamic parameters may also be calculated based on these measurements (e.g., pulmonary vascular resistance [PVR] and cardiac index [CI]). Weight and height will be collected to calculate body surface area (BSA) and index the cardiac output.

While this section describes the optional RHC assessments at Baseline and Week 24, all subjects eligible to participate in this study must either have data available from a historical RHC conducted within three years prior to the start of screening (i.e., date of signing the Informed Consent Form [ICF]), or undergo a RHC during the screening period prior to randomization with results consistent with the diagnosis of PAH as described in Section 4.1.

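### Protocol Section 7 contradicts Section 3 on how the Baseline 6MWT is obtained: the order around a same-day catheterisation and, less sharply, whether the practice walk is optional

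*Protocol*

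**What the plan says.** **Order around the RHC.** Section 7.2 introduces its list with "The recommended sequence of events for the Baseline Visit is displayed below". The first item is "RHC (optional; must be performed within 5 days before randomization (inclusive) and on one stable PAH-approved oral monotherapy". The 6MWT with Borg score is the sixth item, and the laboratory and NT-proBNP draw is the seventh. The window is inclusive, so it covers the day of randomisation.

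Section 3.2.1.6 deals with an RHC on that day explicitly: "all other study-related assessments, other than initiation of study drug, should be performed prior to conduct of the RHC". The walk falls on the same day by design, because Section 3.2.1.2.2 says "A Baseline 6MWT must be performed prior to initiation of study drug and should be conducted on the day of randomization". At Week 24 there is no conflict: Section 3.2.1.6, Section 7.3 and Table 3-1 footnote h all place the RHC after the other assessments.

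**Practice walk.** For subjects with no earlier 6MWT at the site, Section 3.2.1.2.1 says "a practice 6MWT must be conducted at least 1 day prior to the Randomization 6MWT for applicable subjects", and Table 3-1 footnote c says "a practice 6MWT must be conducted during the Screening period". The Section 7.1 checklist reads "Practice 6MWT/Borg dyspnea score (*optional*; serves as a practice test if the subject has not previously performed this test at the study site". It does not repeat the one-day gap, and 7.1 also allows Screening and Baseline to be done in a single visit.

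**The concern.** Coordinators are likely to work from the visit checklists in Section 7. A site that follows 7.2 literally on a day with both procedures catheterises first and walks afterwards. The same site, following 7.3, walks before the RHC at Week 24. The two walks behind the change score would then be taken under different conditions. The Baseline NT-proBNP sample, which feeds the second formally tested secondary endpoint, would also follow the RHC. Separately, a site that takes the word optional in 7.1 at face value may record a first-ever walk as the Baseline.

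One Baseline 6MWD value has several uses:

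- It is the reference for the 15% fall and for the any-decrease criterion, both components of the primary endpoint (Protocol 2.1).
- It decides the 150 m entry limit (Protocol 4.1) and the 350 m randomisation stratum (Protocol 5.2). The stratum also enters the primary log-rank test (SAP 10.1.1.2).
- It defines the Week 24 change and is the covariate in its analysis (SAP 10.2.1).

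It must be measured before study drug starts, so it cannot be repeated once the subject has been dosed.

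**Working it through.** **Step 1. Compare the texts.**

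| Item | Section 3 and Table 3-1 | Section 7 |
|---|---|---|
| RHC on day of randomisation | 3.2.1.6: all other assessments first | 7.2: RHC first, 6MWT sixth, NT-proBNP seventh; no same-day exception |
| RHC at Week 24 | 3.2.1.6 and footnote h: after the other assessments | 7.3: after the other assessments |
| Practice walk, no earlier walk at site | 3.2.1.2.1 and footnote c: mandatory | 7.1: optional, with the no-earlier-test condition in the same bullet |
| Gap between practice and Baseline walk | 3.2.1.2.1 and 3.2.1.2.2: at least one day | 7.1: not stated |

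For an RHC before the day of randomisation, the 7.2 order is simply chronological and there is no conflict. For an RHC on that day, 7.2 and 3.2.1.6 cannot both be followed.

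**Step 2. Effect on the worsening criteria if the Baseline is recorded too low.** The documents give no size for any after-effect of catheterisation or of a missing practice walk. The understatement *d* is therefore an assumption.

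- 15% criterion: the recorded threshold is 0.85 × (1 − *d*) of the true Baseline, so the true fall needed is 1 − 0.85 × (1 − *d*).
  - *d* = 3%: 1 − 0.85 × 0.97 = 17.6%
  - *d* = 5%: 1 − 0.85 × 0.95 = 19.3%
  - *d* = 10%: 1 − 0.85 × 0.90 = 23.5%
- Any-decrease criterion: the true fall must exceed *d* itself, that is 3%, 5% or 10%.
- In metres, taking 333 m as an illustrative true Baseline (the mean in TDE-PH-308, Protocol 1.2.4): the correct threshold is 0.85 × 333 = 283 m. Recorded 20 m too low, it becomes 0.85 × 313 = 266 m, a true fall of 1 − 266/333 = 20.1%.

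**Step 3. Effect at the cut-offs, same assumption.**

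- Stratum: true Baselines above 350 m and up to 350/0.95 = 368 m (*d* = 5%) or 350/0.90 = 389 m (*d* = 10%) would be recorded in the lower stratum.
- Entry limit: true Baselines from 150 m to just under 150/0.95 = 158 m or 150/0.90 = 167 m would be recorded as ineligible.

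**Step 4. Relation to the stated power.** Protocol 10.2 gives at least 90% power with 205 events and a hazard ratio of 0.62. The Schoenfeld formula reproduces this: Φ(½ × √205 × |ln 0.62| − 1.960) = Φ(1.46) = 92.8%. Baseline 6MWD is not an input, so the stated figure is untouched by this point.

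**The case against.** The strongest reply is that Section 3 remains in force. Section 3.2.1.6 is a specific rule for the same-day case, 7.2 is only a recommended order, and a specific rule normally governs a general list. On that view 7.2 merely lacks a cross-reference. Likewise, the 7.1 bullet carries its own condition ("serves as a practice test if the subject has not previously performed this test at the study site"), so optional can be read as applying to subjects who already have a walk at the site. Both arguments have force. A reader might infer that the checklists cancel the Section 3 requirements; they do not. They contradict them. The practice-walk conflict is the softer of the two. The RHC argument does not remove the problem, because 7.2 expressly allows the day of randomisation and then gives an order that 3.2.1.6 rules out.

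The second reply is that the reach is small. The RHC conflict touches only subjects in the optional hemodynamic sub-study who are catheterised on the day of randomisation at a site that overlooks 3.2.1.6. The practice-walk conflict touches only subjects with no earlier walk at the site. Death, PAH hospitalisation and prostacyclin initiation do not use Baseline 6MWD. This stands in full.

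The third reply is that the error is not differential. The Baseline walk precedes randomisation, so its error should be similar in both arms, and the Week 24 model adjusts for Baseline 6MWD. SAP Section 6 keeps the stratum used at randomisation even if it is later found wrong, so the stratified test stays valid. This also stands.

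**Conclusion.** The point holds as an inconsistency in the site instructions for a measurement that cannot be repeated once dosing starts. The RHC order is the main part and the practice-walk label the lesser part. In affected subjects, an understated Baseline would make walk-based worsening register later or not at all, and could put some on the wrong side of 150 m or 350 m. The 19.3–23.5% range rests entirely on the assumed 5–10% understatement. The documents support neither that figure nor any estimate of how many subjects are affected, so no trial-level effect can be stated.

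Two stronger readings are tempting.

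- **A biased or diluted treatment comparison.** The documents do not show this. An error made before randomisation is expected to be alike in both arms, so the supportable harm is lost sensitivity and noise.
- **Setting the possible shift in a subject's Week 24 change against the earlier trials' effects.** At 333 m, a 5–10% understatement is 17–33 m, which looks large beside the +10 to +23 m reported in Protocol 1.2.4. That comparison is not valid. The first is a within-subject shift expected in both arms, and the second are placebo-corrected differences.

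**What to change.** - **Section 7.2:** reconcile with 3.2.1.6 so that one order applies when the RHC is on the day of randomisation, and state that order in the checklist itself. The reconciliation should take in Section 7.3 and Table 3-1 footnote h, so that the Baseline and Week 24 walks are taken under comparable conditions.
- **Section 7.1:** reconcile with 3.2.1.2.1 and Table 3-1 footnote c by replacing the word optional with a statement that the practice walk is required if the subject has no earlier 6MWT at this site, at least one day before the Baseline walk.

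The cost is wording in two checklists and a note to sites. No procedure, visit or analysis is added. No new eCRF item is needed, because the 6MWT listing in SAP 10.2.1 already covers circumstances that adversely affected a walk.
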